7.2.4.2 Events of Clinical Interest

Selected non-serious and serious adverse events are also known as Events of Clinical Interest (ECI) and must be recorded as such on the adverse event case report forms/worksheets and reported within 2 working days to UPMC HCC ([name] ([contact]) and [contact]), who will forward to

Merck Global Safety. (Attn: Worldwide Product Safety; [contact]).

Events of clinical interest for this trial include:

1. An overdose of Merck product, as defined in Section 7.2.1 that is not associated with clinical symptoms or abnormal laboratory results.
2. An elevated AST or ALT lab value that is greater than or equal to 3X the upper limit of normal AND an elevated total bilirubin lab value that is greater than or equal to 2X the upper limit of normal AND at the same time, an alkaline phosphatase lab value that is less than 2X the upper limit of normal, as determined by way of protocol-specified laboratory testing or unscheduled laboratory testing.
3. In the event a subject develops any of the following AEs, a detailed narrative of the event should be reported as an ECI to Merck Global Safety within 2 working days of the event:
 - grade \geq 3 diarrhea
 - grade \geq 3 colitis
 - grade \geq 2 pneumonitis
 - grade \geq 3 hypo- or hyperthyroidism

Potential skin events of clinical interest:

Every attempt should be made by the study team to take photographs of the actual ECI skin lesion or rash as soon as possible. If affected, photographs should be taken of:

- the head (to assess mucosal or eye involvement)
- the trunk and extremities
- a close-up of the skin lesion/rash.

If possible, a ruler should be placed alongside the site of the skin occurrence as a fixed marker of distance.

- The time/date stamp should be set in the 'ON' position for documentation purposes.
- Photographs should be stored with the subject's study records.
- Merck may request copies of photographs.

In addition to the photographs, the following documents from the Merck Pembrolizumab Program Event of Clinical Interest Guidance Document (at the end of the protocol) need to be completed and sent to UPMC HCC ([name] ([contact]) and [contact]), who will forward to Merck Global Safety (Attn: Worldwide Product Safety, [contact]) within 2 business day of the subject's presentation with the dermatologic event:

- Appendix 2—Past Medical History Related to Dermatologic Event
- Appendix 3—Presentation of the Dermatologic Event

- Appendix 4—Focused Skin Examination

A separate guidance document has been provided in the appendix entitled “Event of Clinical Interest and Immune-Related Adverse Event Guidance Document.” This document provides guidance regarding identification, evaluation and management of ECIs and irAEs.

Additional ECIs are identified in this guidance document and also need to be reported to Merck Global Safety within 2 working days of the event.

Subjects should be assessed for possible ECIs prior to each dose. Lab results should be evaluated, and subjects should be asked for signs and symptoms suggestive of an immune-related event. Subjects who develop an ECI thought to be immune-related should have additional testing to rule out other etiologic causes. If lab results or symptoms indicate a possible immune-related ECI, then additional testing should be performed to rule out other etiologic causes. If no other cause is found, then it is assumed to be immune-related.

ECIs that occur in any subject from the date of first dose through 90 days following cessation of pembrolizumab treatment, or the initiation of a new anticancer therapy (whichever is earlier) whether or not related to pembrolizumab, must be reported to Merck Global Safety within 2 working days.

7.2.5 Evaluating Adverse Events

An investigator who is a qualified physician will evaluate all adverse events according to the NCI Common Terminology for Adverse Events (CTCAE), version 5.0. Any adverse event which changes CTCAE grade over the course of a given episode will have each change of grade recorded on the adverse event case report forms/worksheets.

All adverse events regardless of CTCAE grade must also be evaluated for seriousness.

Table 12. Evaluating Adverse Events

An investigator who is a qualified physician, will evaluate all adverse events as to:

V4.0 CTCAE Grading	Grade 1	Mild; asymptomatic or mild symptoms; clinical or diagnostic observations only; intervention not indicated.
	Grade 2	Moderate; minimal, local or noninvasive intervention indicated; limiting age-appropriate instrumental ADL.
	Grade 3	Severe or Medically Significant but not immediately life-threatening; hospitalization or prolongation or hospitalization indicated; disabling; limiting self-care ADL.
	Grade 4	Life Threatening consequences; urgent intervention indicated.
	Grade 5	Death related to AE
Seriousness	A serious adverse event is any adverse event occurring at any dose or during any use of the investigational condition that:	
	† Results in death; or	
	† Is life threatening; or places the subject, in the view of the investigator, at immediate risk of death from the event as it occurred (Note: This does not include an adverse event that, had it occurred in a more severe form, might have caused death.); or	
	† Results in a persistent or significant disability/incapacity (substantial disruption of one's ability to conduct normal life functions); or	
	† Results in or prolongs an existing inpatient hospitalization (hospitalization is defined as an inpatient admission, regardless of length of stay, even if the hospitalization is a precautionary measure for continued observation. (Note: Hospitalization [including hospitalization for an elective procedure] for a preexisting condition which has not worsened does not constitute a serious adverse event.); or	
	† Is a congenital anomaly/birth defect (in offspring of subject exposed to the investigational condition regardless of time to diagnosis); or	
	Other important medical events that may not result in death, not be life threatening, or not require hospitalization may be considered a serious adverse event when, based upon appropriate medical judgment, the event may jeopardize the subject and may require medical or surgical intervention to prevent one of the outcomes listed previously (designated above by a †).	
Duration	Record the start and stop dates of the adverse event. If less than 1 day, indicate the appropriate length of time and units.	
Action Taken	Did the adverse event cause the study treatment to be discontinued?	
Relationship to Test Condition	Did the investigational condition cause the adverse event? The determination of the likelihood that the investigational condition caused the adverse event will be provided by an investigator who is a qualified physician. The investigator's signed/dated initials on the source document or worksheet that supports the causality noted on the AE form, ensures that a medically qualified assessment of causality was done. This initialed document must be retained for the required regulatory time frame. The criteria below are intended as reference guidelines to assist the investigator in assessing the likelihood of a relationship between the test drug and the adverse event based upon the available information. The following components are to be used to assess the relationship between the investigational condition and the AE; the greater the correlation with the components and their respective elements (in number and/or intensity), the more likely the investigational condition caused the adverse event (AE):	
	Exposure	Is there evidence that the subject was actually exposed to the investigational condition such as: reliable history, acceptable compliance assessment (pill count, diary, etc.), expected pharmacologic effect, or measurement of drug/metabolite in bodily specimen?
	Time Course	Did the AE follow in a reasonable temporal sequence from administration of the investigational condition? Is the time of onset of the AE compatible with a study-induced effect (applies to trials with investigational medicinal product[s])?
	Likely Cause	Is the AE not reasonably explained by another etiology such as underlying disease, other drug(s)/vaccine(s), or other host or environmental factors?

Relationship To Investigational Condition (continued)	The following components are to be used to assess the relationship between the test condition and the AE: (continued)	
	Dechallenge	Was the investigational condition discontinued or dose/exposure/frequency reduced? If yes, did the AE resolve or improve? If yes, this is a positive dechallenge. If no, this is a negative dechallenge.
		
(Note: This criterion is not applicable if: (1) the AE resulted in death or permanent disability; (2) the AE resolved/improved despite continuation of the investigational condition; or (3) the trial is a single-exposure trial; or (4) The test condition is/are only used one time.)

	Rechallenge	Was the subject re-exposed to the test condition in this study? If yes, did the AE recur or worsen? If yes, this is a positive rechallenge. If no, this is a negative rechallenge.
		
(Note: This criterion is not applicable if: (1) the initial AE resulted in death or permanent disability, or (2) the trial is a single exposure trial); or (3) The test condition is/are used only one time).

		
NOTE: IF A RECHALLENGE IS PLANNED FOR AN ADVERSE EVENT WHICH WAS SERIOUS AND WHICH MAY HAVE BEEN CAUSED BY THE INVESTIGATIONAL CONDITION, OR IF REEXPOSURE TO THE INVESTIGATIONAL CONDITION POSES ADDITIONAL POTENTIAL SIGNIFICANT RISK TO THE SUBJECT, THEN THE RECHALLENGE MUST BE APPROVED IN ADVANCE BY THE MERCK U.S. CLINICAL MONITOR AS PER DOSE MODIFICATION GUIDELINES IN THE PROTOCOL.

	Consistency with Trial Treatment Profile	Is the clinical/pathological presentation of the AE consistent with previous knowledge regarding the test condition?
The assessment of relationship will be reported on the case report forms /worksheets by an investigator who is a qualified physician according to his/her best clinical judgment, including consideration of the above elements.		
Record One of the Following	Use the following scale of criteria as guidance (not all criteria must be present to be indicative of a test condition relationship).	
Yes, there is a reasonable possibility of test condition relationship.	There is evidence of exposure to the test condition. The temporal sequence of the AE onset relative to the administration of the test condition is reasonable. The AE is more likely explained by the test condition than by another cause.	
No, there is not a reasonable possibility of test condition relationship	Subject was not exposed to the test condition OR temporal sequence of the AE onset relative to administration of the test condition is not reasonable OR there is another obvious cause of the AE. (Also entered for a subject with overdose without an associated AE.)	

7.2.6 Sponsor Responsibility for Reporting Adverse Events

All Adverse Events will be reported to regulatory authorities, IRB/IECs and investigators in accordance with all applicable global laws and regulations.

8.0 STATISTICAL ANALYSIS PLAN

8.1 Statistical Analysis Plan Summary

This study will test the efficacy of reirradiation combined with pembrolizumab, administered at 200mg IV every 3 weeks, in patients with unresectable locoregional recurrence or second primary head and neck squamous cell carcinoma. In addition, the early toxicity profile and safety of the combination of the mAb with radiation therapy will be established.

This is a single-arm phase II trial with continuous monitoring of acute non-hematologic toxicity. The primary efficacy endpoint is Progression-Free Survival (PFS). The efficacy outcome of the study will be summarized by the median time to progression or death. This will be related to experience reported in the literature.

While the safety profile of pembrolizumab is well established when giving the drug as a single agent, the safety of the combination of pembrolizumab with high dose ionizing radiation needs to be established. In case the defined boundary for the incidence of severe non-hematologic toxicity is crossed, the trial will be stopped, and the available data at that point will be carefully reviewed in order to suggest potential modification of the drug-radiation combination that may warrant testing in a future, independent trial.

8.2 Statistical Analysis Plan

The design includes 1) continuous toxicity monitoring in the first 20 patients enrolled and 2) evaluation of toxicity and efficacy after the pre-specified target sample size is reached and the efficacy data have matured.

8.2.1. Continuous Toxicity Monitoring in the First 20 Patients Enrolled (Stopping rule)

The endpoint is severe (grade 4-5), non-hematologic toxicity that occurs during the radiation therapy plus 2 weeks (i.e. within the first 7 weeks of trial treatment). Based on the literature review, grade 4-5 acute radiation toxicity occurs in <20% of radiation-drug combinations tried in the reirradiation setting for SCCHN. Early stopping for unexpected, severe toxicity is based on continuous monitoring of grade 4-5 non-hematologic toxicity with the aim of keeping the probability of early stopping at around 5% if the true underlying rate of this toxicity is 20%. Following Ivanova et al.⁸³ we use the boundary proposed by Pocock.⁸⁴ If $\geq b_k$ patients with toxicity have been observed after enrolling the first k patients, then the study will be stopped as detailed above. Values of b_k for the current design are given in Table 13.

Table 13. Pocock boundary for early stopping due to excessive grade 4+ toxicity with a probability of stopping of about $\phi = 0.05$ and assuming the true toxicity rate is $\theta_0 = 0.2$

[figure not shown]
k	1	2	3	4	5	6	7	8	9	10	11	12	13	14	15	16	17	18	19	20
b_k	—	—	3	4	4	4	5	5	5	6	6	6	7	7	7	8	8	8	9	9

It is important for the validity and practical implementation of this strategy that the sequence of patients entered into the study is strictly recorded and preserved. Ideally, the design assumes that the outcome, i.e. the incidence of grade 4+ toxicity among the first i patients is known when entering patient $i+1$. However, the accrual rate is expected to be around two patients per month, and the time window for observing early toxicity in a patient is pragmatically defined as the time during and within two weeks after the completion of RT. Therefore, insisting on complete observations before entering the next patient will slow down accrual considerably. Instead we will allow staggered entry of cases. For patient safety reasons, no more than 5 patients will be allowed to be undergoing or be within 2 weeks of completing reirradiation treatment at any point during the enrollment of the first 20 patients.

At the time when the boundary is crossed, the treatment with pembrolizumab will be discontinued in all patients on treatment at that point in time and toxicity data will be reviewed by the DSMB (Data and Safety Monitoring Board).

If 20 patients are enrolled and have completed therapy (radiation plus 2 weeks) without crossing the toxicity boundary, toxicity data from those patients will be reported and reviewed by the DSMB. No further accrual will occur until after DSMB review. All subsequent accrual will be continued with respect to the efficacy question and although there will be no further toxicity boundary halting the study, toxicity will still be recorded and reported for the whole phase II cohort.

Fig. 1. Hypothetical example of the timeline for enrolling and recording toxicity in the first 5 patients. At time t_1 , 2 of the first 3 patients have developed grade 4+ toxicity and the trial should continue. At this point in time 3/4 and 3/5 patients have developed relevant toxicity and the boundary for stopping accrual at this dose level is still not crossed. At time t_2 , 4 of the first 4 patients enrolled have developed grade 4+ toxicity which means accrual should stop at this point in time. The status of the 5th patient at time t_2 does not affect the decision as to whether the boundary is crossed or not.

An impression of the statistical power of the initial continuous toxicity monitoring phase may be achieved from a specific example. If 2 out of 20 patients develop grade 4+ early toxicity, the estimated incidence is 10%, and the upper limit of the exact 1-sided 95% confidence interval is 28%.

8.2.2 Primary Efficacy Analysis

All patients entered are evaluable with respect to the efficacy endpoint, which is the main trial endpoint. The primary endpoint is progression-free survival (PFS). Based on the literature review presented in the background section, we assume that reirradiation without pembrolizumab produces a median PFS of 8 months.

The expected accrual rate is 2 patients per month for a total of 48 evaluable patients. A 12-month maturation period after completing accrual has been added. All patients will be included in efficacy analysis irrespective of the dose of drug or radiation actually received. This follows a strict intention-to-treat principle. Subjects eligible for replacement are discussed in section 5.10. We will use a 1-sided test with a 5% significance level (α) to test the uni-directional hypothesis that the median PFS is prolonged from 8 to 12 months by combining anti-PD-1 mAb with reirradiation. We estimate that the power (1- β) of the study is 78%. The efficacy result will be summarized as a median PFS with a 1-sided 95% confidence interval. No early stopping rule for futility is planned due to the relatively rapid enrollment of patient in relation to the expected median PFS.

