1.0 TRIAL SUMMARY

Abbreviated Title	Reirradiation combined with pembrolizumab (trade name: Keytruda®) in recurrent SCCHN
Trial Phase	Phase II
Clinical Indication	Locoregional recurrence or second primary SCCHN which is unresectable or the patient is unwilling to undergo resection who are able to undergo reirradiation
Trial Type	Interventional
Type of Control	NA-historical
Route of Administration	Intravenous
Trial Blinding	Unblinded
Treatment Groups	Single arm trial
Number of Trial Subjects	48 evaluable subjects
Estimated Duration of Trial	The estimated time from opening the trial to data analysis is approximately 36 months. This allows for accrual over 24 months and a minimum 12 month maturation period for all patients enrolled.
Duration of Participation	
Each subject will participate in the trial from the time the subject signs the Informed Consent Form (ICF) through the final protocol-specified evaluation. Each patient will undergo screening and then be treated with reirradiation with 1.2 Gy BID, 5 days a week (weeks 1-5). Pembrolizumab will be given at 200mg intravenous every 3 weeks starting day one or day two of reirradiation and will be continued in all patients until 3 months post completion of reirradiation, at which time a PET/CT will be done to evaluate response. Patients with progressive disease (PD) will be taken off the study. Patients that have a complete response (CR) will be followed clinically and radiographically, and if disease recurs may be eligible to be retreated with pembrolizumab for up to one year. Patients with partial response (PR) or stable disease (SD) will continue treatment with pembrolizumab for up to two years unless one of the following occurs:
 
 --documented confirmed disease progression --unacceptable adverse event(s) --intercurrent illness that prevents further administration of treatment --investigator decision to withdraw the subject --subject withdraw of consent --subject pregnancy --subject noncompliance --administrative reasons (i.e. trial is closed prematurely). 
Patients who have not progressed at completion of 24 months of therapy will be observed, but may be eligible for 1 year of retreatment with pembrolizumab if they develop recurrence/progression if they qualify as detailed in the protocol and if the trial is still ongoing.

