4.2 Rationale

4.2.1 Rationale for the Trial and Selected Subject Population

Squamous cell carcinoma of the head and neck (SCCHN) is the 6th most common malignancy worldwide.²⁵ For patients with locally advanced SCCHN, radiation is part of either initial definitive therapy or adjuvant therapy after surgical resection. Despite aggressive initial definitive therapy, patients with SCCHN are at high risk for the development of second primary tumors and a significant proportion of patients will recur, commonly within the first 2 years.²⁶,²⁷ The majority of these recurrences are locoregional and are associated with significant pain, disfigurement, and functional decline.²⁸ Unfortunately, a significant proportion of these patients will not have a salvage surgical option. Even with salvage surgery, local failure rates are upwards of 59%.²⁹

Patients with locoregional recurrence or second primary without a surgical option are currently treated with reirradiation with concurrent chemotherapy. Reported outcomes from the largest trials that evaluated reirradiation with concurrent chemotherapy include a median PFS of 7-8 months and median OS of 10-12 months,³⁰⁻³³ with even worse survival in patients who recurred within a year compared to patients recurring more than one year after primary radiation (median OS 5.8 vs. 9.8 months respectively, $p = .036$).³ Improved outcomes are desperately needed for this patient population.

While concurrent chemotherapy is given with reirradiation, there is no data evaluating whether concurrent therapy improves outcome compared to reirradiation alone. Additionally, various chemotherapy regimens including Cisplatin/Paclitaxel, 5FU/hydrea, Docetaxel, Cisplatin/Docetaxel have been used concurrently without direct comparison of effectiveness and there is not one chemotherapy regimen that can be regarded as standard of care.³⁰⁻³⁵

Traditional chemotherapy sensitizes the tissue to radiation allowing for increased efficacy when given concurrent with radiation. However, this sensitization comes at the cost of increased hematologic and non-hematologic toxicity. In trials with reirradiation concurrent with chemotherapy for recurrent SCCHN, grade 4 and 5 acute toxicity rates are 16-23% and upwards of 5% respectively in the largest trials.^{30-32, 34}

The PD-L1:PD-1 Pathway in SCCHN

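### Does leaving the PFS test unnamed in section 8.2.2 undermine the stated 78% power?

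*Combined protocol and SAP*

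**What the plan says.** Section 8.2.2 holds the whole primary efficacy analysis. The benchmark is fixed there: "we assume that reirradiation without pembrolizumab produces a median PFS of 8 months". The decision is framed as a test: "We will use a 1-sided test with a 5% significance level", whose purpose is to "test the uni-directional hypothesis that the median PFS is prolonged from 8 to 12 months by combining anti-PD-1 mAb with reirradiation". Power is given as 78%, with 48 evaluable patients accrued at two per month and 12 months of maturation after accrual. The trial summary (section 1.0) gives the same timetable: "This allows for accrual over 24 months and a minimum 12 month maturation period for all patients enrolled".

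The reporting sentence comes after the test: "The efficacy result will be summarized as a median PFS with a 1-sided 95% confidence interval". Section 8.1 uses the same verb: "The efficacy outcome of the study will be summarized by the median time to progression or death", and adds that the result will be set against published experience. Section 8.2.3 defines PFS and its censoring. None of these sections names the test statistic, the assumed survival distribution or the method for the median's confidence interval.

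**The concern.** The hypothesis is worded in medians and the only output described is a median with a one-sided limit. An analyst could therefore compute a Kaplan-Meier median, take the nonparametric 95% lower limit, and call the trial positive if that limit exceeds 8 months. Everyone has at least 12 months of potential follow-up, so without dropout nobody is censored before month 8. That rule then reduces to counting patients progression-free at 8 months, and it ignores all later events. A log-rank or exponential test uses them.

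The two routes could differ by 20 to 30 percentage points of power and reach opposite verdicts in a sizeable share of trials. This is an open-label, single-arm trial with a historical comparator, so a method chosen after the data are seen would be a real weakness.

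**Working it through.** **Inputs.** From section 8.2.2: one-sided alpha 0.05, null median 8 months, alternative 12 months, n = 48, two patients per month. From sections 1.0 and 8.2.2: 24 months of accrual and 12 months of further follow-up. Assumed, because the plan does not state them: exponential PFS, uniform accrual, no loss to follow-up, and progression observed when it occurs.

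**Step 1. Reproduce the 78%.**

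- Hazard under the alternative: λ = ln 2 / 12 = 0.05776 per month.
- Probability of an event by the analysis: 1 − (e^(−12λ) − e^(−36λ)) / (24λ) = 1 − (0.500 − 0.125)/1.3863 = 0.7295.
- Expected events: 48 × 0.7295 = 35.0. The same formula at a median of 8 months gives 40.9.
- Power of the log-hazard test: Φ(ln 1.5 × √35.0 − 1.645) = Φ(0.754) = 77.5%.

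Simulation under the same assumptions gives:

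| Test | Power at 12 months | Type I error at 8 months |
|---|---|---|
| Exponential log-hazard (Wald) | 78.4% | 4.1% |
| One-sample log-rank, variance E | 78.6% | 4.2% |
| One-sample log-rank, variance (O+E)/2 | 81.3% | 5.2% |

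Here O and E are the observed and expected events. The plan's figure matches the first two tests.

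**Step 2. The nonparametric median rule.** With exponential PFS and a 12-month median, the proportion progression-free at 8 months is 0.5^(8/12) = 0.630; under the null it is 0.5. Exact binomial, n = 48:

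| Rule | Interval it corresponds to | Type I error | Power |
|---|---|---|---|
| At least 30 of 48 | linear, log or arcsine | 5.57% | 59.2% |
| At least 31 of 48 | log-log | 2.97% | 47.4% |

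Interpolated to a type I error of 4.1%, close to that of the log-rank test, power is about 52%. Discreteness therefore explains only part of the gap. At a true 12-month median, the log-rank test and this rule disagree in about 26% (30 of 48) or 35% (31 of 48) of simulated trials.

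**Step 3. Does the gap depend on exponential PFS?** The table uses Weibull PFS with the stated median. The log-rank test (variance E) still refers to the hazard ln 2 / 8.

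| Weibull shape | Log-rank type I error, median 8 | Log-rank power, median 12 | Median-rule power, median 12 |
|---|---|---|---|
| 0.8 | about 19% | 85% | 34–45% |
| 0.9 | about 10% | 82% | 41–53% |
| 1.0 | about 4% | about 78% | 47–59% |
| 1.2 | 0.4% | 70% | 61–72% |
| 1.5 | below 0.1% | 52% | 78–86% |

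The median rule's type I error stays at about 3% to 6% in every row, because it depends only on the proportion progression-free at 8 months.

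**Step 4. Which rule does the text adopt?** The test and its level come first in section 8.2.2, and the median with its interval follows as a summary. No sentence compares the interval with 8 months.

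**The case for a change.** The strongest case for a change is that prespecification is the main safeguard in an uncontrolled, open-label trial. A 5% level implies rejection at p<0.05, but not the p-value of which test. The toxicity rule in section 8.2.1 names its method and gives its full boundary, so the thinner efficacy text stands out. The fix would be a few sentences, with no effect on sample size or visits.

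Part of this stands. The statistic, its variance form, the exponential assumption and the interval method are all unstated, and no other section supplies them. Naming them would make the plan easier to reproduce.

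It does not show that the plan is underpowered or wrong. The 47% to 59% requires replacing the stated test with an interval rule. Nor is either method plainly better. Section 4.2.1 reports that historical results "include a median PFS of 7-8 months and median OS of 10-12 months", which are medians only, so the shape of the historical curve cannot be judged from the documents. The log-rank test gains power if PFS is exponential and loses control of type I error if the hazard falls over time. The median rule holds its type I error in the scenarios examined but has less power under exponential PFS.

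**Conclusion.** No change follows. The stated 78% is correct for 48 patients and about 35 events under exponential PFS, using either an exponential log-hazard test or a one-sample log-rank test with variance E. An analyst who looks for the one-sided 5% test that fits the stated medians, timetable and power arrives at one of these, and reports the median with its interval beside it. That is a gap sensibly filled from what is already on the page.

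The lower power of 47% to 59% (about 52% at matched type I error) applies only if a nonparametric limit decides success and PFS is exponential. At Weibull shape 1.2 the two approaches are roughly level (70% against 61–72%), and at shape 1.5 the order reverses (52% against 78–86%). Read as a choice of method, the point is a fair trade-off. All these figures assume uniform accrual, no dropout and progression observed when it occurs. Progression is in fact found largely at scheduled scans, so actual operating characteristics may differ for both methods.
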